Rationale for metabolome and microbiome as endpoints. The 2020-2030 NIH Strategic Plan for Nutrition Research³⁴ calls for mechanistic studies on the relationship between foods and both the microbiome and the metabolome to allow a systems approach to nutrition research, a strategy recognized as valuable by the NIH and nutrition research community.^{32, 33} Both the metabolome and microbiome are sensitive to short-term changes in diet, as shown by us and others.^{53-55, 58-62} Further, both outcomes are needed for a full complement of systems-wide nutritional effects. Evidence suggests that dietary patterns,⁶³⁻⁶⁸ individual foods, nutrients or food groups^{62, 69-76} may display a unique metabolome or microbiome signature, including for meat and fish consumption.⁷⁵ However, many of these analyses were cross-sectional, associating baseline diet with baseline biospecimens, leaving the potential for confounding and the inability to draw causal inference. Further rationale for the microbiome endpoint is evidence that meat may expand certain bacterial groups in the colon and evidence that specific microbial metabolites are generated from the hydrolysis of meat-derived aromatic and sulfur containing amino acids.^{55, 77} Moreover, red meat derived heme induces genotoxic microbial H₂S and nitrite production using *narG*, the first step in genotoxic reactions leading to DNA adducts.⁷⁷ Finally, poor diet quality (lower HEI scores) in an observational study was linked to enrichment of two microbial species, *Enterobacter* and *Escherichia-Shigella*, that reduce nitrate to nitrite using nitrate reductase (*narG*),^{78, 79} findings relevant for Aim 2 as we will do 16S rRNA sequencing and identify microbial functional genes, including *narG*.

This study has the following primary **specific aim**:

1. Identify the extent and nature of shifts in the metabolome when consuming a standard HEI-2015 diet compared to a HEI-2015-M diet.

Hypothesis 1: Daily intake of red and processed meat will induce shifts in the metabolome detected in blood and urine samples using various metabolomics platforms.

This study has the following **secondary aim**

[figure not shown]
2. Identify and characterize modulation of the gut microbial community when consuming a standard HEI-2015 diet compared to a HEI-2015-M diet.

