7. DATA ANALYSIS PLAN

This trial identifies (1) the extent and nature of metabolomic shifts and (2) as a secondary aim, modulation of the gut microbiome when consuming a standard HEI-2015 diet compared to a HEI-2015-M diet. We expect that daily intake of red and processed meat will induce shifts in the metabolome detected in blood and urine samples, and secondarily in the gut microbiome detected in extracted fecal DNA. Under the NIH R21 mechanism, it is considered a preliminary trial.

Statistical Analysis for the Primary Aim. Aim 1 identifies metabolomic markers that differ between HEI-2015 and HEI-2015-M. Metabolites from NMR and LC/MS-MS platforms will be used to allow greater coverage of the metabolome and as shown feasible by [name] and others.⁹⁸ Metabolite levels are normalized by dividing by the batch's median value followed by removing metabolites with >25% CVs in the embedded blinded duplicates as well as those with >20% missing values (expected at 5-10% of total). Next, we will use unsupervised principal components analysis (PCA) to visually examine the data patterns and variability. We then apply supervised orthogonal partial least squares discriminant analysis (OPLS-DA) to identify candidate biomarkers that may differ by diet arm. VIP (variable importance in projection) scores >2 will be retained. For each identified metabolite, separate linear mixed models will be fit to examine fold-changes in end of diet period metabolite levels by HEI-2015 and HEI-2015-M, adjusting for baseline. In the cross-over design each participant is their own control, minimizing noise in intra-individual variation in endogenous metabolites. The cross-over design also minimizes confounding by age, BMI, and diet order, but models are run with and without these adjustments. The Benjamini-Hochberg approach controls for false discovery rate (FDR) <0.10.⁹⁹

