Statistical Analysis for the Secondary Aim. To account for different sequencing depths, we will initially apply the centered-log ratio (CLR) transformation to each sample after replacing any zero counts by 1 or a small imputed value.¹⁰⁴ We will first gauge the overall strength of microbial signal by applying a microbiome-wide kernel-association test fusing a GLMM-MiRKAT¹⁰⁵ with respect to the weighted UniFrac distance.^{106, 107} Analyses will account for the crossover study design using linear mixed models with outcome of either genera, alpha diversity, or genes for butyrate kinase (*buk*) or nitrate reductase (*narG*), adjusting for baseline. As with Aim 1, we will conduct analyses with and without adjustment for age, BMI, diet order and other covariates. We will use Benjamini-Hochberg approach to account for FDR <0.10.⁹⁹ Based on our studies⁶² and that of others⁵⁸ we expect to have 80% power to detect β coefficients in the linear mixed models in the range of 0.3- 04 for differences between diets at $p < 0.05$. Primary analysis focuses on three genera associated with butyrate production and three genera associated with nitrate reduction. All genera will be examined in exploratory analysis.¹⁰⁸

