7.1 Sample Size for the Primary Aim

The sample size is based on the primary aim. For this pilot trial with a fixed sample size of 20 participants, we estimate that we expect to have 80% power to detect fold changes between diets of ± 0.20 for blood and urine metabolites. Power calculations used MetSizeR.¹¹⁰ Tests are 2-sided $\alpha = 5\%$.

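### The primary analysis has no valid test of Hypothesis 1 (that meat shifts the metabolome); its only inference is a BH list on metabolites pre-screened with the same diet labels

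*Combined protocol and SAP*

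**What the plan says.** Section 1 states Hypothesis 1 globally: "Daily intake of red and processed meat will induce shifts in the metabolome detected in blood and urine samples using various metabolomics platforms".

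Section 7 (primary aim), repeated in the synopsis, gives the analysis in this order:

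1. After normalisation and QC filtering, "unsupervised principal components analysis (PCA) to visually examine the data patterns and variability".
2. Supervised OPLS-DA on diet arm, after which "VIP (variable importance in projection) scores >2 will be retained".
3. "For each identified metabolite, separate linear mixed models will be fit to examine fold-changes in end of diet period metabolite levels", adjusting for baseline, with and without age, BMI and diet order.
4. "The Benjamini-Hochberg approach controls for false discovery rate (FDR) <0.10".

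No p-value or permutation test is attached to the PCA or the OPLS-DA. The BH family is not defined (blood and urine together or apart; all metabolites or only those past the screen), and neither the adjusted nor the unadjusted model is named as deciding.

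The secondary aim in the same section does have an overall step: "We will first gauge the overall strength of microbial signal by applying a microbiome-wide kernel-association test".

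Section 7.1 says "Tests are 2-sided" at alpha 5%, within the power statement for fold changes in blood and urine metabolites.

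**The concern.** BH at 0.10 controls the expected share of false entries on a list of metabolites. That suits the question of which metabolites moved. It does not supply a test, at a stated level, of whether the metabolome moved at all. Because the plan gives no rule for judging Hypothesis 1, the conclusion can be settled after the list is seen.

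The order of the steps makes this worse. The VIP screen uses the same diet labels and the same data as the models that follow, so the p-values that reach BH have already been selected for being small. A non-empty list then says little about whether diet had any effect.

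The trial is a pilot meant to support a larger grant application. Whether the metabolome responded is the finding most likely to be carried forward.

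**Working it through.** **The plan's own figure.** Section 7.1 states 80% power for a fold change of ±0.20 with 20 participants, two-sided 5%. It cannot be reproduced, because no SD, metabolite count or FDR setting is given. Solving backwards for a single paired comparison, SD of the within-person difference = 0.20 × √20 / (1.96 + 0.84) ≈ 0.32 (0.30 with the t distribution). The 5% therefore fits a per-metabolite calculation. It is not tied to a decision on Hypothesis 1.

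**Inputs from the documents.** 20 participants, each on both diets; VIP cut-off 2; BH at 0.10; blood and urine.

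**Assumptions.** 50, 150 or 500 metabolites per fluid; correlation 0 to 0.8; intraclass correlation mainly 0.5 (0.2 and 0.7 also tried); VIP from one predictive component. The rule examined, at least one BH hit, is a hypothetical reading of the plan.

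**Step 1: BH over all metabolites, no diet effect.** Every discovery is then false, so the FDR equals the chance of any discovery. With independent metabolites:

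- one family: 0.10
- two families: 1 − 0.90² = 0.19
- three families, if the faecal metabolites of section 5.1.1 were added: 1 − 0.90³ = 0.27

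**Step 2: BH after the screen, no diet effect.** With one component, VIP² for a metabolite is its squared covariance with diet divided by the average over metabolites. VIP > 2 is therefore roughly |z| > 2, which has probability 0.0455 under the null. For 300 metabolites that predicts 300 × 0.0455 = 13.7 passing, and the simulation gave 13.7. A |t| of 2 on 19 degrees of freedom has two-sided p = 0.06. BH on k survivors rejects all of them if the largest p is at most 0.10, so nearly everything that passes the screen also passes BH.

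Simulated chance of at least one hit with no diet effect (1,000 to 2,000 runs each):

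| Metabolites per fluid; correlation | BH all, one family | BH all, two families | VIP > 2 then BH, one family | VIP > 2 then BH, two families |
|---|---|---|---|---|
| 50; none | 0.100 | 0.193 | 0.972 | 0.993 |
| 150; none | 0.096 | 0.187 | 0.996 | 1.000 |
| 150; 0.5 in blocks of 10 | 0.088 | 0.186 | 0.977 | 0.998 |
| 150; 0.6 throughout | 0.067 | 0.122 | 0.641 | 0.731 |
| 500; 0.6 throughout | 0.045 | 0.085 | 0.568 | 0.692 |

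Over all runs, including separate runs at 100 and 200 metabolites per fluid, the ranges were about 5-11%, 9-21% and (after the screen) 57-100%.

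**Step 3: power.** 300 metabolites, random signs, 600 runs. The global tests swap diet labels within participant and test at 5%. Entries are for independent metabolites / blocks of 10 at 0.5 / all at 0.3.

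| Shift (in SD of the difference) | Any BH hit, all metabolites, one family | Sum of t² | Max \|t\| |
|---|---|---|---|
| none | 0.09 / 0.09 / 0.10 | 0.04 / 0.04 / 0.06 | 0.04 / 0.05 / 0.06 |
| 20% by 0.2 | 0.24 / 0.18 / 0.15 | 0.50 / 0.25 / 0.08 | 0.15 / 0.09 / 0.09 |
| 50% by 0.2 | 0.36 / 0.34 / 0.32 | 0.99 / 0.75 / 0.12 | 0.20 / 0.19 / 0.20 |
| 50% by 0.3 | 0.77 / 0.73 / 0.62 | 1.00 / 1.00 / 0.47 | 0.47 / 0.46 / 0.40 |
| 2% by 0.9 | 0.95 / 0.95 / 0.94 | 0.85 / 0.59 / 0.12 | 0.86 / 0.87 / 0.88 |

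The BH column is not at the 5% level (see its first row), so the comparison favours it somewhat. The global tests hold their size. The sum of t² is strong for dense shifts unless all metabolites share a correlation, and max |t| is strong for sparse ones.

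**The case against.** The strongest reply is that Aim 1 is an identification aim, that FDR control is the usual tool for it, and that an R21 pilot promises no yes/no verdict. Much of this stands. The plan nowhere says that a BH hit decides Hypothesis 1, and BH over all metabolites giving about 10% under a complete null is BH working at its declared level. But the protocol does state a hypothesis about the whole metabolome, and the screen before BH means that even the identification list lacks the FDR control it claims.

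Three stronger readings are tempting and are not supported:

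- A reader might infer that the primary hypothesis is tested at a multiple of a promised 5%. The 5% stands only in the sample-size section and promises nothing about Hypothesis 1.
- A reader might infer that the plan would often miss a diffuse shift. That holds only for small shifts with BH over all metabolites (15-36% detected at 0.2 SD with 20-50% shifted, one family). In the order written, every shifted trial simulated produced a hit, so the difficulty there is false support.
- A reader might infer that the secondary aim has a deciding test. Its kernel test gauges overall signal, and the analysis called primary there concerns six genera. The contrast shows only that the team uses an omnibus step for one aim and not the other.

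It is also fair to object that a sum-of-t² test should not decide alone. With 30% of metabolites shifted by 0.3 SD and correlation shared by all, its power was 0.10-0.17 against 0.32-0.45 for BH over all metabolites. It is weak for sparse shifts too. The fix takes this into account.

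**Conclusion.** The point holds in this form: Hypothesis 1 has no valid test and no stated rule for judging it, and the BH step follows a screen that uses the same diet labels. That rests on the text alone.

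The sizes are conditional. If any BH hit were read as support, the chance of false support with no diet effect is about 57-100% as written, about 5-11% with BH over all QC-passing metabolites in one family, and about 9-21% with two families. The 0.10 and 0.19 for independent metabolites are exact. The remaining figures depend on assumed metabolite counts and correlations, and the screened figures also on a one-component VIP. A change is worth making before the data are analysed; it does not call the trial design into question.

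**What to change.** In section 7 and the synopsis:

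1. Add one pre-specified global test of Hypothesis 1 over all QC-passing blood and urine metabolites, before any VIP screen. Use log-scale end-of-diet differences within participant, HEI-2015-M minus HEI-2015, with a stated rule for missing values, since metabolites with up to 20% missing are retained. Section 4.6 provides one baseline shared by both periods, so it cancels: (Y_M − bX) − (Y_H − bX) = Y_M − Y_H.
2. Take the p-value from re-randomising diet order within participant, following the allocation scheme actually used, at two-sided 5%.
3. Fix the statistic in advance so that it responds to dense and sparse shifts. One option is the smaller of the sum-of-t² and max-|t| p-values, calibrated within the same permutations. The power of this combination was not simulated here.
4. Keep BH at FDR 0.10 to identify which metabolites moved, over all QC-passing blood and urine metabolites as one family. Use VIP for description only.
5. State that neither a BH list alone nor a non-significant global test alone proves shift or no shift.

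The cost is a short addition to the SAP and a permutation script on samples already planned. The downside is that any single global statistic loses power for some patterns; the sum of t² does so when shifts are sparse or when all metabolites are strongly correlated.

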7.1 Sample Size for the Primary Aim

The sample size is based on the primary aim. For this pilot trial with a fixed sample size of 20 participants, we estimate that we expect to have 80% power to detect fold changes between diets of ± 0.20 for blood and urine metabolites. Power calculations used MetSizeR.¹¹⁰ Tests are 2-sided $\alpha = 5\%$.

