SUBJECT SELECTION CRITERIA: Exclusion Criteria	Exclusion Criteria : 1. Known allergy to red or processed meat 2. Vegetarian or vegan 3. Religious or personal reason(s) to avoid red or processed meat 4. Pregnant and/or exclusively breastfeeding 5. Alcohol or recreational drug abuse

DURATION OF SUBJECT PARTICIPATION AND DURATION OF STUDY	Subjects will participate in the study for 11 weeks. The total duration of the study is expected to be 1.5 years
PRIMARY ENPOINTS	Primary Aim 1: Compare intervention effect of each feeding period on shifts in the metabolome as detected in blood and urine samples relative to baseline for each participant.
SECONDARY ENDPOINTS	Secondary Aim: Compare intervention effect of each feeding period on shifts in the gut microbial community as detected by 16S rRNA gene sequencing and digital droplet PCR relative to baseline for each participant.
STATISTICS Primary Analysis Plan	Statistical analysis for primary Aim 1 (metabolome). Aim 1 identifies metabolomic markers that differ between HEI-2015 and HEI-2015-M. Metabolites from NMR and LC/MS-MS platforms will be combined to allow greater coverage of the metabolome. Metabolite levels are normalized by dividing by the batch's median value followed by removing metabolites with >25% CVs in the embedded blinded duplicates as well as those with >20% missing values (expected at 5-10% of total). Next, we use unsupervised principal components analysis (PCA) to visually examine the data patterns and variability. We then apply supervised orthogonal partial least squares discriminant analysis (OPLS-DA) to identify candidate biomarkers that may differ by diet arm. VIP (variable importance in projection) scores >2 will be retained. For each identified metabolite, separate linear mixed models are fit to examine fold-changes in end of diet period metabolite levels by HEI-2015 and HEI-2015-M, adjusting for baseline. In the cross-over design each participant is their own control, minimizing noise in intra-individual variation in endogenous metabolites. The cross-over design also minimizes confounding by age, BMI, and diet order, but models are run with and without these adjustments. The Benjamini-Hochberg approach controls for false discovery rate (FDR) <0.10.

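### The 80% power in Section 7.1 is not tied to the rule that declares metabolites (VIP >2, then Benjamini-Hochberg at 0.10), and the set of tests over which the FDR is controlled is not stated

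*Combined protocol and SAP*

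**What the plan says.** **Power (Section 7.1).** With the sample size fixed at 20, "we estimate that we expect to have 80% power to detect fold changes between diets of ± 0.20 for blood and urine metabolites". The software is named ("Power calculations used MetSizeR") and the only error rate is an alpha of 5% ("Tests are 2-sided"). No SD, fold-change scale, number of metabolites, share expected to change or target FDR is given. Nothing in the section appears to be redacted.

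**Decision rule (Section 7, primary aim; the synopsis has the same steps).** After quality control and PCA:

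1. "We then apply supervised orthogonal partial least squares discriminant analysis (OPLS-DA) to identify candidate biomarkers that may differ by diet arm".
2. "VIP (variable importance in projection) scores >2 will be retained".
3. "For each identified metabolite, separate linear mixed models will be fit", adjusted for baseline. The synopsis has "For each identified metabolite, separate linear mixed models are fit to examine fold-changes in end of diet period metabolite levels".
4. "The Benjamini-Hochberg approach controls for false discovery rate (FDR) <0.10".

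Neither place says which set of tests BH is counted over. Because models are fitted only to identified metabolites, the natural reading is the VIP-kept set.

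**Use of the figure.** The synopsis rationale for the number of subjects rests n = 20 on being able to see an effect within a fixed R21 budget, and says that the pilot is to support an R01.

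**The concern.** A reader of Section 7.1 will take the 80% as the chance that a metabolite with a ±0.20 fold change is declared. That chance depends on passing VIP >2 and then BH, and the plan does not give it. The 80% is the only numerical support for the primary aim.

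The error rate raises a second question. OPLS-DA ranks metabolites by how well they separate the diet labels, and the mixed models then test the same labels in the same samples. P-values that survive such a filter are already small, so BH applied to them alone has little left to remove. If few metabolites truly change, a sizeable share of the declared markers could be false, and these would feed the R01 planning.

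**Working it through.** **1. The plan's own figure.** With 20 within-person pairs and a paired t-test (19 df), power = P(|T| > t(0.975; 19)), where T is noncentral t with noncentrality d√20. Setting power to 0.80 gives d = 0.660 (normal approximation 0.626). The implied SD of the within-person difference depends on the unstated scale:

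- effect ln 1.20 = 0.182: SD = 0.182/0.660 = 0.276
- effect 0.20 on the analysis scale: SD = 0.20/0.660 = 0.303
- effect −ln 0.80 = 0.223: SD = 0.223/0.660 = 0.338

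The documents give none of these SDs. For a difference of 0.20, power at 0.05 is 92% at SD 0.25, 81% at 0.30, 56% at 0.40 and 40% at 0.50. So 80% is attainable, but it can only be back-solved.

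**2. Set-up for the decision rule (all assumptions).** 20 pairs; 300 independent autoscaled metabolites; within-person correlation 0.5; every changed metabolite has d = 0.660. One-component PLS on the 40 end-of-diet samples stands in for OPLS-DA, with VIP = √m·|w| for m metabolites and unit weight vector w. A paired t-test stands in for the mixed model. Section 4.6 provides a single baseline for both periods, so with complete data it does not alter the within-person contrast. BH is at 0.10.

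For BH on all metabolites with no VIP step, the large-m threshold t solves t = 0.10·[(1−π)t + π·power(t)], where π is the share changed. At π = 0.05, t = 0.0015 and power is 0.275. Check: 0.10·(0.95×0.0015 + 0.05×0.275) = 0.0015.

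**3. Results.**

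| Share changed | VIP >2, BH on kept set: power | Same: realised FDR | VIP >2, BH over all QC-passing: power | BH on all, no VIP: power |
|---|---|---|---|---|
| 2% | 75–78% | 62–67% | not run | 12% |
| 5% | 69% | 34% | 30–31% | 28% |
| 10% | 56% | 12% | 39–41% | 43% |
| 20% | 33% | 2% | 31–34% | 59% |
| 30% | 18% | <1% | 18% | 67% |

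The 2% row covers 100, 300 and 1000 metabolites with correlation 0.3 or 0.7. The last column is the large-m value; simulation with 300 metabolites gave 20% at 2% changed and 30–31% at 5%. In the fourth column, realised FDR was no more than about 10% throughout.

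**4. Why the kept-set column behaves this way.** The VIP step does the work: 99.7–100% of kept metabolites pass BH, and the median BH cut-off is 0.10. Mean VIP² is 1, so at most a quarter of metabolites can have VIP >2. Equal effects therefore crowd each other out as more metabolites change. With no true change, about 99% of runs declare at least one metabolite (98–100% over the settings tried). With BH counted over all metabolites, that figure was about 11%.

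**5. Sensitivity, BH on the kept set.**

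- Across 100 or 1000 metabolites, correlation 0.3 or 0.8, person-centred data and correlated blocks of 10, power was 66–71, 52–57, 27–34 and 10–19% at 5, 10, 20 and 30% changed.
- With unequal SDs and no autoscaling (Section 7 mentions only division by the batch median), power was 44, 37, 25 and 19%, and FDR 41, 24, 11 and 5%.
- With two- or three-component VIP, power at 5% changed was 63–64%.
- With SD 0.20 and a ×1.20 effect (97% power at 0.05), power was 91, 78, 44 and 18%, and FDR 17, 3, 0.1 and 0%.

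**The case against.** The strongest reply is that no error in the 80% has been shown. That stands. A reader might infer that the true power is below 80%, but the documents do not support this. The SD is unknown, and with SD 0.20 the kept-set rule reaches 91% at 5% changed. BH on all metabolites gives 82% if 70% change. MetSizeR may also have been run to an FDR target; its title in the reference list describes an analysis-based approach, and no settings are reported. The back-solved 0.660 assumes that the 80% is a per-metabolite figure at 5%.

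A reader might also infer that the plan's BH step fails to control FDR. That is too strong. The family is not named; when BH is counted over all QC-passing metabolites, FDR stayed at or below about 10%. Even on the kept set, FDR was far below 0.10 when 20–30% changed. The supported statement is that control is not assured.

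Finally, this is a preliminary pilot with n fixed by budget, and the simulated figures rest on assumed inputs. Both points stand, and they limit the consequence. They do not remove the mismatch between Section 7.1 and Section 7, which is visible without any simulation. Naming the software does not show that the VIP step was modelled.

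**Conclusion.** The point holds as a gap between the power statement and the decision rule, together with an unspecified BH family. The 80% is neither confirmed nor contradicted; it is not shown to be the probability that a ±0.20 metabolite is declared. On the natural reading, with BH on the VIP-kept set, the stated FDR <0.10 is not assured. In the illustration, realised FDR was about a third at 5% changed and about two thirds at 2%, but 2% or less at 20% and above.

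These sizes assume independent metabolites, equal effects, a one-component PLS stand-in and effects with exactly 80% power at 0.05. Scaling and component choices move them. The text mismatch and the missing inputs rest on none of these assumptions. This should be fixed; it does not call n = 20 into question.

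**What to change.** Keep n = 20 and make two changes to the text.

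1. **Section 7 and the synopsis: name the BH family.** State that BH at 0.10 is counted over all metabolites that pass quality control, with VIP >2 used as a descriptive or additional filter. If BH is to stay on the VIP-kept set, replace the FDR control statement with one saying that FDR <0.10 is not assured, because selection and testing use the same diet labels.
2. **Section 7.1: say what the 80% refers to.** Give the fold-change scale, the assumed SD of the within-person difference, the MetSizeR settings, and the error rate used (nominal 5% or an FDR target). Add simulated power and realised FDR for the chosen rule over a stated range of shares changed, for example 2 to 30%.

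If the MetSizeR settings cannot be recovered, say that the 80% has not been shown to apply to the VIP and BH rule. Do not label it as nominal per-metabolite power, since that would put an unverified statement into the protocol.

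The cost is rewording and a short simulation; participants and procedures do not change. The downside is that the stated power may look less favourable. If BH is counted over all metabolites, fewer will be declared when few change.
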